## **107. SUBSTUDY ASSESSMENTS**

Every effort should be made to ensure that the required procedures are completed as described. However it is anticipated that from time to time there may be circumstances, outside of the control of the investigator that may make it unfeasible to perform a procedure. In these cases the investigator will take all steps necessary to ensure the safety and well-being of the subject. When a required procedure cannot be performed the investigator will document the reason for this and any corrective and preventive actions which he or she has taken to ensure that normal processes are adhered to as soon as possible. The study team will be informed of these incidents in a timely fashion.

### **107.1. Surgeon's Assessment of Procedural Difficulty**

Following the total joint replacement surgery, the orthopedic surgeon performing the surgery will be asked to answer the following question:

“Taking into consideration the subject's medical history and physical condition prior to surgery would you classify the operative procedure as:

- Uneventful; or
- Minor complications; or
- Major complications.

If the category of minor or major complications is chosen, the surgeon will be requested to specify the complication(s).

### **107.2. Pathology Specimens**

Surgeons will be requested to ship pathology specimens from the total joint replacement surgery to a Central Laboratory for analysis. Detailed instructions for the shipping of pathology specimens will be provided. Identification of specimens of adequate quality, preparation and histopathologic examination of the specimens will be performed in a standardized manner by the Central Laboratory under the direction of an expert orthopedic pathologist. Pathology reports will generally be returned to the referring site within 7-10 days following completion of the report by the Central Laboratory.

### **107.3. Telephone-based Assessments**

Post-surgery, subjects will be contacted monthly via telephone by study site personnel.

#### **107.3.1. Adverse Events**

At each post-surgery telephone contact, subjects will be queried for the occurrence of adverse events. All adverse events reported by the subject must be recorded on the appropriate case report form (CRF).

Subjects reporting adverse events (any seriousness or severity) with preferred terms of bradycardia, syncope, orthostatic hypotension, anhidrosis or hypohidrosis should be further evaluated for the presence of sympathetic autonomic neuropathy. Subjects will be referred

for neurologic or cardiologic evaluation depending on symptom presentation and the investigator's assessment as to the specialist best able to evaluate the subject.

### **107.3.2. Concomitant Analgesic Medication**

At each post-surgery telephone contact, subjects will be queried about concomitant analgesic medication usage including dose, dosing regimen and reason for use. This information should be recorded on the appropriate case report form (CRF).

### **107.3.3. Physical Rehabilitation Activities**

At the Week 4, 12 and 24 post-surgery telephone contacts, subjects will be queried for physical rehabilitation activities related to the replaced joint. Specifically, subjects will be asked to respond yes or no to the following question:

“Are you participating in physical rehabilitation activities related to your replaced joint?”

Subjects will be queried for details if the answer to the question is yes. This information should be recorded on the appropriate case report form (CRF).

### **107.3.4. Additional or Corrective Procedures**

At the Week 12 and 24 post-surgery telephone contacts, subjects will be queried for additional or corrective procedures related to the total joint replacement surgery. Specifically, subjects will be asked to respond yes or no to the following question:

“Have you been told by your orthopedic surgeon that additional or corrective procedures (for example a revision or implant replacement) are necessary for your total joint replacement?”

Subjects will be queried for details if the answer to the question is yes. If necessary, the orthopedic surgeon may be contacted to confirm/expand upon the information regarding additional or corrective procedures.

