### **8.7. Hospitalization**

Hospitalization is defined as any initial admission (even less than 24 hours) in a hospital or equivalent healthcare facility or any prolongation of an existing admission. Admission also includes transfer within the hospital to an acute/intensive care unit (eg, from the psychiatric wing to a medical floor, medical floor to a coronary care unit, or neurological floor to a tuberculosis unit). An emergency room visit does not necessarily constitute a hospitalization; however, the event leading to the emergency room visit should be assessed for medical importance.

Hospitalization does not include the following:

- Rehabilitation facilities;
- Hospice facilities;
- Respite care (eg, caregiver relief);
- Skilled nursing facilities;
- Nursing homes;
- Same-day surgeries (as outpatient/same-day/ambulatory procedures).

Hospitalization or prolongation of hospitalization in the absence of a precipitating, clinical AE is not in itself an SAE. Examples include:

- Admission for treatment of a preexisting condition not associated with the development of a new AE or with a worsening of the preexisting condition (eg, for workup of persistent pre-treatment laboratory abnormality);
- Social admission (eg, subject has no place to sleep);
- Administrative admission (eg, for yearly physical examination);

- Protocol-specified admission during a study (eg, for a procedure required by the study protocol);
- Optional admission not associated with a precipitating clinical AE (eg, for elective cosmetic surgery);
- Hospitalization for observation without a medical AE;
- Preplanned treatments or surgical procedures. These should be noted in the baseline documentation for the entire protocol and/or for the individual subject;

Diagnostic and therapeutic noninvasive and invasive procedures, such as surgery, should not be reported as AEs. However, the medical condition for which the procedure was performed should be reported if it meets the definition of an AE. For example, an acute appendicitis that begins during the AE reporting period should be reported as the AE, and the resulting appendectomy should be recorded as treatment of the AE.

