### **102.2. Endpoints**

The following endpoints will be assessed in this substudy:

- Surgeon's Assessment of Procedural Difficulty: number and percentage of surgeries assessed as uneventful, minor complications or major complications.
- Subjects' overall satisfaction with surgery as assessed by the Self-Administered Patient Satisfaction (SAPS) Scale: number and percentage of subjects satisfied versus unsatisfied with their total joint replacement at Week 24.
- Number and percentage of subjects with a post-surgical complication(s) up to Week 24 (derived from reported adverse events).
- Number and percentage of subjects with additional or corrective procedures related to their total joint replacement up to Week 24.
- Number and percentage of subjects participating in physical rehabilitation activities related to the replaced joint up to Week 24.
- Change from Baseline to Week 24 in average pain in the replaced joint.
- Change from Baseline to Week 24 in WOMAC Pain, Stiffness and Physical Function subscales in the replaced joint (subjects undergoing total hip or knee replacement surgery only).
- Change from Baseline to Week 24 in the SPADI in the replaced shoulder (subjects undergoing total shoulder replacement surgery only).
- Concomitant analgesic medication use.

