### **103. SUBSTUDY STUDY DESIGN**

This substudy is a long-term observational study of subjects from tanezumab Study A4091061 (regardless of treatment group) who undergo a total knee, hip or shoulder replacement during participation in the study (Treatment Period or Safety Follow-Up period). If while the subject is participating in this substudy, the subject undergoes an additional total joint replacement surgery or the site becomes aware that an additional total joint replacement surgery has been scheduled for the subject, the subject will be requested to provide information on the additional total joint replacement surgery as well. Finally, any subject with a qualifying total joint replacement after the last subject completes the treatment period in study A4091061 may be followed in study A4091064 which is a separate study with a design similar to this substudy.

This substudy is designed with a total duration of subject follow-up of 24 weeks after the total joint replacement surgery. There will be two methods of data collection utilized in this substudy: interview by site staff via the telephone and IWRS accessed by desktop, laptop or tablet computer (or paper if the subject has no access to the internet via a desktop, laptop or tablet computer). Following the surgery, the subject will be contacted monthly via telephone by study site personnel to ascertain whether the subject has experienced any adverse events and to record any concomitant analgesic medications the subject is taking as well as the reason for the medication use. An assessment of the subject's overall satisfaction with their

total joint replacement (IWRS), average pain in the replaced joint (IWRS), the subject's level of function and activity in the replaced joint (IWRS) and physical rehabilitation activities (telephone interview) will be made at Weeks 4, 12 and 24. At Weeks 12 and 24, subjects will be queried during the telephone interview as to whether any additional or corrective procedures related to the total joint replacement are planned.

Any subject who expresses a desire to leave this substudy before 24 weeks of follow-up have been completed should be asked to complete all assessments scheduled for Week 24.

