### **109.2. Analysis of Endpoints**

Data from the substudy of subjects with total joint replacement of the knee, hip or shoulder will be presented at substudy Baseline or Day 1 (day of surgery) and each post-surgery visit using observed data (no imputation for missing data), and at Week 24 using Last Observation Carried Forward (LOCF) for missing data. Data will be shown at the time points specified and also using change from (pre-surgery) Baseline where relevant. Data will be shown overall, and split by treatment group.

For the Surgeon's Assessment of Procedural Difficulty, the number and percentage of subjects in each category (Uneventful, Minor complications, Major complications) will be presented. Complications reported by the surgeon will be listed.

For the Subject's Overall Satisfaction with Surgery assessments (using the Self-Administered Patient Satisfaction scale, SAPS), the responses [score] for each category (Very Satisfied [100], Somewhat Satisfied [75], Somewhat Dissatisfied [50], Very Dissatisfied [25]) will be summarized for each of the four items. The scale score is the un-weighted mean of the scores from the individual items, ranging from 25 to 100 per item with higher scores indicating greater satisfaction. This total score will be summarized. Responses to the question "How satisfied are you with the results of your surgery?" will also be summarized as satisfied (very satisfied and somewhat satisfied categories combined) and dissatisfied (somewhat dissatisfied and very dissatisfied categories combined).

Similarly, the number and percentage of subjects who have required (i) additional or corrective procedures related to their total joint replacement and (ii) participating in physical rehabilitation activities related to their replaced joint will be presented.

Average pain (NRS) in the replaced joint for all subjects, WOMAC Pain, Stiffness and Physical Function sub-scale scores for subjects who had total knee or hip replacement and SPADI Pain, function and total score for subjects who had total shoulder replacement will be summarized (including change from substudy Baseline summaries).

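### The scripted substudy questions on corrective procedures and rehabilitation do not reliably measure the endpoints in Section 102.2

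*Protocol*

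**What the plan says.** The protocol describes the corrective-procedure item in four ways within Appendix 16:

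- **Endpoint, Section 102.2:** "Number and percentage of subjects with additional or corrective procedures related to their total joint replacement up to Week 24".
- **Design, Section 103 (and the substudy summary):** subjects are asked at Weeks 12 and 24 "as to whether any additional or corrective procedures related to the total joint replacement are planned".
- **Scripted question, Section 107.3.4:** "At the Week 12 and 24 post-surgery telephone contacts" the subject gives a yes or no to "Have you been told by your orthopedic surgeon that additional or corrective procedures (for example a revision or implant replacement) are necessary" for the total joint replacement. Details are sought only after a yes, and contacting the surgeon is optional.
- **Analysis, Section 109.2:** the report gives "the number and percentage of subjects who have required (i) additional or corrective procedures related to their total joint replacement".

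For rehabilitation, the Section 102.2 endpoint is "Number and percentage of subjects participating in physical rehabilitation activities related to the replaced joint up to Week 24". The script in Section 107.3.3, used at Weeks 4, 12 and 24, is "Are you participating in physical rehabilitation activities related to your replaced joint", again with details only after a yes. The visit instructions in Sections 106.3, 106.5 and 106.8 are wider: they have sites query rehabilitation since the operation and, at Weeks 12 and 24, query for additional or corrective procedures in general terms.

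**The concern.** Having a procedure, having one planned, being told that one is necessary and having required one are different events. A subject can satisfy one description and not another, so the reported proportion depends on which description the site and the programmer follow. The script settles in practice what is collected, and it contains no item on whether a procedure was carried out or on what date.

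The rehabilitation question has a related weakness. The endpoint covers a period, while the question takes a reading at three points in it.

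Repeat surgery bears directly on why the substudy exists. Its summary says the data address whether subjects treated with tanezumab have a different post-surgical outcome, as part of a risk-characterization package agreed with the regulator. The data are to be combined with similar data from other tanezumab studies. Section 109 leaves detailed methods to an analysis plan, but such a plan cannot recover information that was never requested from the subject.

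**Working it through.** The protocol gives no figure for this point, so there is none to reproduce. The check sets question against endpoint and adds one illustration on assumed inputs.

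**Corrective procedures, three cases**

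1. *Told that a revision is necessary, not operated on by Week 24.* The scripted answer is yes. The subject has no event under Section 102.2 as worded, but fits the wording of Section 109.2 and possibly that of Section 103.
2. *Revised before the Week 12 call, nothing further needed.* The subject has the Section 102.2 event. Because the question looks back to what the surgeon has said, the natural answer is yes. Because it speaks of procedures that are necessary now, no is also an honest answer, and the detail query is then not triggered.
3. *Revised, and answers yes.* The answer alone does not separate this subject from case 1. Performance and date depend on free-form details.

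Weight of one misclassification: the expected enrolment is below 25, and 1/25 = 4%, so each subject moves the overall proportion by more than 4 percentage points, and by more again within a treatment group.

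**Rehabilitation, illustration**

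Input from Section 107.3.3: calls at v = 4, 12 and 24 weeks. Assumptions, not from the protocol: a single course of L weeks, start time s uniform over Weeks 0 to S, the question answered literally, and call windows ignored. A course is seen if s ≤ v ≤ s + L for some call, that is, if s lies in [v − L, v].

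For S = 12:

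- L = 2: seen for s in [2, 4] and [10, 12], 4 of 12 weeks; missed 8/12 = 67%.
- L = 4: seen for [0, 4] and [8, 12], 8 of 12; missed 4/12 = 33%.
- L = 6: seen for [0, 4] and [6, 12], 10 of 12; missed 2/12 = 17%.
- L = 8 or more: none missed.

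For S = 20:

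- L = 2: 4 of 20 weeks seen; missed 80%.
- L = 4: 8 of 20 seen; missed 60%.
- L = 6: [0, 4], [6, 12] and [18, 20], 12 of 20 seen; missed 40%.
- L = 8: [0, 12] and [16, 20], 16 of 20 seen; missed 20%.
- L = 12: none missed.

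For S = 2, a course of 4 weeks or more is always seen, while a 2-week course is missed. The loss is therefore confined to short or late courses.

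**The case against.** The strongest reply is that other parts of the protocol fill most of the gap.

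- *The question looks back.* Asking what the subject has been told includes the past, so most revised subjects would say yes. This stands. It reduces omissions but does not separate performed from recommended procedures.
- *Section 106 prompts are broader.* True for both items. But Section 107.3 gives the specific words to be used, and sites following one section rather than the other would collect different things.
- *Need is close to the analysis wording.* Section 109.2 does sit nearer to the script than Section 102.2 does. That shows the endpoint itself needs one definition.
- *Adverse event reporting.* A reader might infer from "Diagnostic and therapeutic noninvasive and invasive procedures, such as surgery, should not be reported as AEs" in Section 8.7 that a revision never reaches the safety data. The documents do not support that. The same paragraph has the underlying condition reported where it meets the adverse event definition, and its example records the operation as treatment of that event. Section 108 applies Section 8 to the substudy, and adverse events are queried at all six calls. What remains is that Section 102.2 derives only the complications endpoint from adverse events and gives no such route for corrective procedures.
- *Small and descriptive.* Section 109.1 expects fewer than 25 subjects and no inference. This stands and limits the weight of the point.

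**Conclusion.** The point holds in a limited form: the scripts capture related quantities but do not reliably measure the Section 102.2 endpoints. For procedures, a yes can count an operation that was not performed, and a no remains possible after one that was. For rehabilitation, a short course lying between calls can be missed, while a course of at least 4 weeks begun in the first 2 weeks would be seen.

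The number of subjects affected cannot be derived from the protocol. The miss rates above depend on assumed start times and lengths and are not predictions. It would go too far to say that completed revisions are generally lost or that rehabilitation between calls is never recorded, because the look-back wording, the Section 106 prompts and adverse event records would recover many cases.

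The consequence is confined to a descriptive substudy and the pooled data to which it contributes. The main trial's primary endpoint is not affected.

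**What to change.** Define each endpoint once, and bring the substudy summary and Sections 103, 107.3 and 109.2 into line with Section 102.2.

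- **Section 107.3.4:** at the existing Week 12 and Week 24 calls, ask whether, since the operation or the last time the question was asked, any additional or corrective procedure on the replaced joint was performed (with its date) or only recommended. Record the two separately and count performed procedures for the Section 102.2 endpoint.
- **Section 107.3.3:** at the existing Week 4, 12 and 24 calls, ask whether any rehabilitation for the replaced joint took place since the operation or the last time the question was asked. This also matches Section 106.

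The cost is two reworded questions and one extra case report form field, with no added call or visit. The one drawback is comparability: the data will be combined with similar data from other tanezumab studies, so the answer to the present told-necessary item should stay identifiable in the new form.

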## **107.4. Web-based Assessments**

### **107.4.1. Overall Satisfaction with Joint Replacement Surgery**

The Self-Administered Patient Satisfaction Scale (SAPS) evaluates subject satisfaction with the outcome of hip and knee arthroplasty and was designed to be used in conjunction with other clinical measures and functional health status instruments to evaluate the results of hip and knee arthroplasty.

The scale consists of four items focusing on satisfaction with the extent of pain relief, improvement in ability to perform home or yard work, ability to perform recreational activities and overall satisfaction with joint replacement.

Specifically, subjects will be asked to respond to the following questions:

- How satisfied are you with the results of your surgery?
- How satisfied are you with the results of your surgery for improving your pain?

- How satisfied are you with the results of surgery for improving your ability to do home or yard work?
- How satisfied are you with the results of surgery for improving your ability to do recreational activities?

Items are scored on a 4-point Likert scale with response categories consisting of ‘very satisfied’ (100 points), ‘somewhat satisfied’ (75 points), ‘somewhat dissatisfied’ (50 points), and ‘very dissatisfied’ (25 points). The scale score is the unweighted mean of the scores from the individual items, ranging from 25 to 100 per item with higher scores indicating greater satisfaction.

Subjects will be requested to complete the SAPS at Weeks 4, 12, and 24 either via the IWRS or by paper if the subject does not have access to the internet via a desktop, laptop or tablet computer. When completed on paper, the subject will be requested to return the assessment to the site as soon as possible, but no later than 5 days, after completion of the assessment.

#### **107.4.2. Pain in Replaced Joint**

Average pain in the joint to be replaced (pre-surgery) and the replaced joint (post-surgery) will be assessed with an 11-point Numeric Rating Scale (NRS) ranging from zero (no pain) to 10 (worst possible pain).

Question:

Select the number that best describes your average pain in your (joint to be replaced or your replaced joint) the past 24 hours.

0	1	2	3	4	5	6	7	8	9	10
No Pain										Worst Possible Pain

At Baseline and at Weeks 4, 12 and 24 following total joint replacement surgery, subjects will be asked to indicate their average pain in the joint to be replaced (pre-surgery) or the replaced joint (post-surgery) via the IWRS or by paper if the subject does not have access to the internet via a desktop, laptop or tablet computer. When completed on paper, the subject will be requested to return the assessment to the site but no later than 5 days, after completion of the assessment.

#### **107.4.3. Assessment of Functional Activity**

Subjects undergoing total knee or hip replacement will be asked to complete the Western Ontario and McMaster Universities Osteoarthritis Index (WOMAC) with the knee or hip that was replaced serving as the “index joint”. Subjects undergoing total shoulder replacement will be asked to complete the Shoulder Pain and Disability Index (SPADI). Descriptions of these assessments are provided below.

### 107.4.3.1. WOMAC

Subjects who will be proceeding to total knee or hip arthroplasty will be requested to complete all subscales of the WOMAC (ie, pain, physical function and stiffness) at Baseline and Weeks 4, 12, and 24 following total joint replacement surgery either via the IWRS or by paper if the subject does not have access to the internet via a desktop, laptop or tablet computer. When completed on paper, the subject will be requested to return the assessment to the site but no later than 5 days, after completion of the assessment.

A copy of the WOMAC can be found in [Appendix 17](#).

